13.1 CRITERIA FOR REMOVAL FROM STUDY

Subjects may withdraw consent at any time for any reason or be dropped from the trial at the discretion of the investigator should any untoward effect occur. In addition, a subject may be withdrawn by the investigator if enrollment into the trial is inappropriate, the trial plan is violated, or for administrative and/or other safety reasons.

A subject must be discontinued from the trial for any of the following reasons:

- The subject or legal representative (such as a parent or legal guardian) withdraws consent.
- Confirmed radiographic disease progression

Note: A subject may continue on treatment with confirmed radiographic progression if clinically stable or clinically improved.

- Unacceptable adverse experiences
- Intercurrent illness that prevents further administration of treatment
- Investigator's decision to withdraw the subject
- Subject death
- The subject has a confirmed positive serum pregnancy test
- Noncompliance with trial treatment or procedure requirements
- The subject is lost to follow-up

After the end of treatment, each subject will be followed for 30 days for adverse event monitoring (serious adverse events will be collected for 90 days after the end of treatment).

Subjects who discontinue for reasons other than progressive disease will have post-treatment follow-up for disease status until disease progression, initiating a non-study cancer treatment, withdrawing consent or becoming lost to follow-up, for up to 2 years. After documented disease progression, each subject will be followed by telephone for overall survival until death, withdrawal of consent, the end of the study, or 2 years, whichever occurs first.

If consent is withdrawn, the subject will not receive any further investigational product or further study observation.

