1.0 PROTOCOL SUMMARY AND/OR SCHEMA

This is an open-label, single institution, phase Ib/phase II non-randomized trial that evaluates the safety, tolerability and anti-tumor activity of fulvestrant and Debio 1347 in patients with ER+/HER2- metastatic breast cancer (MBC) that are FGFR-amplified (as confirmed by a CLIA certified laboratory). The phase Ib portion will evaluate 2 dose cohorts (80mg (cohort/dose level 1), and one dose de-escalation cohort (60 mg dose level -1) in case dose level 1 is deemed to have intolerable toxicity. Only the dose of Debio 1347 will be de-escalated. Fulvestrant will be administered intramuscularly at standard doses. Total number of patients expected in the phase 1b portion: minimum 4 and maximum 12.

The phase 2 portion will be comprised of an optimal Simon two-stage design to determine the efficacy (defined as clinical benefit rate (CBR): overall response rate (ORR) + Stable disease (SD) \geq 24 weeks) of Debio 1347 plus fulvestrant. Patients enrolled to the phase II portion will be treated at the recommended phase 2 doses (RP2D) identified from the phase Ib portion of the study. Total number of patients expected in the phase 2 portion: minimum 18, maximum 43.

Briefly, patient's eligibility criteria will include: pre/peri/post-menopausal women and men with metastatic ER+/HER2-/FGFR-amplified breast cancer, in first or second line of treatment in the metastatic setting (phase II portion) without prior use of a FGFR inhibitor; ECOG performance status ≤ 1 , normal baseline blood counts and chemistry laboratory profile; and no intercurrent uncontrolled illness. Treatment will be given until disease progression or unacceptable toxicity. To assess the anti-tumor effect of therapy, we will estimate the overall tumor burden at baseline to which subsequent measurements (performed every 8 weeks for the first 6 months and then every 12 weeks thereafter using the Solid Tumor Response Criteria [RECIST] v1.1) will be compared.

Pharmacokinetic and pharmacodynamic data will be obtained throughout the phase Ib/Phase II portion of the study. A baseline biopsy of a metastatic site will be required for all the patients enrolled on the trial, with the acquisition of at least 3 fragments of a core biopsy and in addition archival tissue will also be obtained, whenever available. Tissue will be evaluated for FGFR amplifications by FISH and protein and mRNA expression in collaboration with [name].

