9.1 TREATMENT/INTERVENTION PLAN

This is an open-label, single institution, phase Ib/phase II non-randomized trial that evaluates the safety, tolerability and anti-tumor activity of fulvestrant and Debio 1347 in patients with ER+/HER2- metastatic breast cancer (MBC) that are FGFR-amplified (as confirmed by a CLIA certified laboratory).

The phase I portion of this trial will evaluate 2 dose cohorts (dose level 1 (starting dose level) 80mg Debio 1347, and dose level -1, 60mg Debio 1347). Fulvestrant will be administered at standard doses. Only the dose of Debio 1347 will be de-escalated as per section 4.1.

Phase 2 portion: The phase 2 portion will be comprised of an optimal Simon two-stage design to determine the efficacy of Debio 1347 plus fulvestrant (N: 18 in the first stage with possibility of going on to 43 if 3 out of the first 18 have a CBR \geq 24 weeks). The dosage in the phase 2 portion will be the MTD/RP2D determined in the phase 1b portion (**80mg daily**), except that concomitant prophylaxis for hyperphosphatemia will not be required.

1 cycle: 28 days. Patients will be on treatment until progression of disease or unacceptable toxicity.

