10.1.2 Survival Follow-up

Once a subject experiences confirmed disease progression or starts a new anti-cancer therapy, the subject moves into the survival follow-up phase and should be contacted by telephone or review of patient records every 12 weeks to assess for survival status until death, withdrawal of consent, or the end of the study, whichever occurs first.

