10.1.3 End-of-Treatment Criteria

Treatment with Debio 1347 will continue until any of the following occur:

- Patient withdraws consent.
- Disease progression documented by CT scan, physical exam or other objective method of measurement. An exception could be made for patients who progressed due to brain metastases; patients may continue treatment with Debio 1347 if, in the Investigator's opinion, there was reasonable evidence of ongoing clinical benefit.
- Unacceptable toxicity.
- Pregnancy.
- Patient's interests as judged by the Investigator.
- In the event of a Debiopharm International SA decision to no longer supply study drug, ample notification will be provided so that appropriate adjustments to subject treatment can be made.

Patients who are removed from study treatment due to AEs are to be treated and followed-up according to accepted medical practice. All pertinent information concerning the outcome of such treatment will be recorded.

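### Sections 1.0, 9.1, 10.1.3 and 13.1 give incompatible rules on Debio 1347 after progression, and no section says which visit schedule applies to a patient kept on drug

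*Combined protocol and SAP*

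**What the plan says.** **Treatment after progression**

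- Section 1.0 (Protocol Summary): "Treatment will be given until disease progression or unacceptable toxicity".
- Section 9.1 (Treatment/Intervention Plan): "Patients will be on treatment until progression of disease or unacceptable toxicity". Neither section gives an exception.
- Section 10.1.3 (End-of-Treatment Criteria) lists among the events that end Debio 1347: "Disease progression documented by CT scan, physical exam or other objective method of measurement". It then says: "An exception could be made for patients who progressed due to brain metastases", provided the investigator sees reasonable evidence of continuing benefit.
- Section 13.1 (Criteria for Removal from Study): "A subject must be discontinued from the trial for any of the following reasons". Confirmed radiographic progression is on that list, and under it stands: "Note: A subject may continue on treatment with confirmed radiographic progression if clinically stable or clinically improved".

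**Follow-up after progression**

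- Section 10.1.2 (Survival Follow-up): "Once a subject experiences confirmed disease progression or starts a new anti-cancer therapy, the subject moves into the survival follow-up phase", and the subject "should be contacted by telephone or review of patient records every 12 weeks to assess for survival status".
- Section 13.1 also has a sentence placing each subject on telephone follow-up for survival after documented progression. Neither section mentions a patient who is still taking the drug.
- The schedule of evaluations in Section 10.1 has treatment columns set by cycle, with one column for Cycle 3 onward, then an end-of-treatment column, then 12-weekly follow-up.

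**The concern.** Two sections foresee dosing after progression, but they permit it for different patients, and two others do not permit it at all. Whether a given patient stops the investigational drug then depends on which section the site consults.

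The second difficulty follows from the first. Once a patient is kept on drug after confirmed progression, Section 10.1.2 assigns that patient to survival contact while the schedule of evaluations still has a treatment column for the current cycle. Phosphate, calcium and QTc changes are found by laboratory test and ECG, and the phosphate tables in Section 9.4.3 act on a measured serum level. Section 3.3.4 shows why these tests matter. In the earlier Debio 1347 dose-escalation study (57 patients, 10 to 150 mg daily, not this combination), hyperphosphatemia was reported in 75%, Grade 3 hypercalcaemia was a dose-limiting toxicity at 80 mg, and QTc prolongation was seen in 2 patients. Whether the tests remain required should not be left to inference.

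**Working it through.** No sample size, power or error rate depends on this point, and the plan states no figure to reproduce. The check is to apply each rule to the same patients.

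**Step 1. Who may continue?**

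| Patient | Sections 1.0 and 9.1 | Section 10.1.3 | Section 13.1 |
|---|---|---|---|
| A. Confirmed radiographic progression outside the brain, clinically stable | Stop | Stop | May continue |
| B. Progression due to brain metastases, continuing benefit in the investigator's opinion | Stop | May continue | Once confirmed radiographically, may continue if clinically stable or better |
| C. Progression outside the brain, documented but not yet confirmed | Stop | Stop | This criterion is not yet met |

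Patient A separates Section 10.1.3 from Section 13.1. Patient B separates the two overview statements from both detailed sections. The two permissions also rest on different tests: site of progression plus judged benefit in Section 10.1.3, and clinical condition at any site in Section 13.1. Neither is a summary of the other.

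**Step 2. When does the rule apply?** Section 10.1.3 acts on documented progression, by scan, physical examination or another objective method. Section 13.1 acts on confirmed radiographic progression. Table 2 in Section 12.2.2.1 places confirmation of progression at least 4 weeks later. With 28-day cycles, 4 weeks × 7 days = 28 days, so the two triggers lie at least one full cycle apart. Patient C falls in that interval.

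**Step 3. Which schedule applies to a patient kept on drug?**

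- Section 10.1.2 is triggered by confirmed progression, with no exception for a patient dosed under Section 10.1.3 or 13.1. Its content is contact by telephone or record review every 12 weeks, for survival status.
- The treatment columns in the Section 10.1 schedule are set by cycle and have no cut-off at progression. The footnotes put phosphate and calcium in the chemistry panel and call for an ECG every third cycle after Cycle 3.
- No sentence ranks one above the other for a patient to whom both apply.

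**Step 4. What is tied to treatment and so not in doubt?**

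- Section 10.1 (Follow up visits) has all adverse events recorded up to the end-of-treatment visit. That visit falls about 2 to 4 weeks after the last dose, or before a new anti-cancer treatment if that is sooner.
- Sections 17.3 and 17.3.1 run SAE reporting to 30 days after the last study treatment.
- Section 13.1 counts its own adverse event and SAE windows from the end of treatment.

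The open question is therefore confined to scheduled visits, laboratory tests and ECGs.

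**The case against.** The strongest reply is that the sections fall into a sensible order if read together. Sections 1.0 and 9.1 are one-line overviews, so the operative conflict is between Sections 10.1.3 and 13.1, and the note in Section 13.1 is an exception to its own list item, not a self-contradiction. Survival follow-up stands under the heading for follow-up visits, which opens with the end-of-treatment visit. In the schedule, the follow-up column comes after the end-of-treatment column. The telephone sentence in Section 13.1 stands among text on what happens after treatment. On that reading a patient still on drug stays in the treatment columns, and a competent site would proceed that way. The phosphate and QTc rules in Sections 9.4.3 and 9.4.4 also attach to Debio 1347 treatment and do not end at progression.

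Much of this stands. It makes continued monitoring the likelier intention, and it narrows the main conflict to two sections. It does not remove that conflict: patient A still gets opposite answers. Nor does it supply the missing sentence on schedule. The phosphate and QTc rules respond to a measured value and do not themselves settle whether the routine measurement is still due.

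A reader might go further and infer that adverse event collection stops at progression, or that scheduled safety tests fall to none for anyone treated past it. The documents do not support this. Adverse event and SAE collection runs with treatment, and Section 10.1.2 is silent about a patient still on drug; it does not direct that the tests stop. A reader might also infer that exposure, time to treatment failure and adverse event rates become non-comparable between patients. That is not shown either. Time to treatment failure is not a listed objective and appears only in Section 9.4, for stopping because of toxicity. Toxicity is summarised descriptively in a non-randomised trial.

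**Conclusion.** The inconsistency is real and needs only the text to establish it. For a clinically stable patient with confirmed progression outside the brain, Section 10.1.3 requires Debio 1347 to stop and Section 13.1 allows it to continue. The triggers differ by at least 4 weeks. The overview statements in Sections 1.0 and 9.1 admit neither exception.

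The monitoring point is narrower. The protocol does not say whether scheduled visits, laboratory tests and ECGs apply to a patient kept on drug after confirmed progression, and they could lapse if a site applied Section 10.1.2 literally. That is a risk from unclear wording, conditional on such a reading.

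The size in patients is unknown. Section 9.2.1 records that all phase 1 patients were off study at the time of that amendment, so the issue concerns phase 2. Its maximum of 43 is the enrolment ceiling, not an estimate of how many would be treated past progression. No effect on the clinical benefit rate, PFS or TTP is shown. The point should be corrected because it governs stopping of an investigational drug and the correction is cheap. This review takes no position on which rule is right.

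**What to change.** 1. Reconcile Sections 1.0, 9.1, 10.1.3 and 13.1 into one statement of whether, for whom and on what trigger (documented or confirmed progression) Debio 1347 may continue after progression. The content is for the sponsor to decide. The other sections can then refer to that statement.
2. Reconcile Section 10.1.2 and the telephone follow-up sentence in Section 13.1 with the schedule of evaluations and the follow-up visit text in Section 10.1, so that the protocol states which schedule applies to a patient still receiving Debio 1347 after progression.

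The cost is a wording amendment to five sections (1.0, 9.1, 10.1.2, 10.1.3 and 13.1), checked against the Section 10.1 schedule. The statistical design does not change. Whether any visits are added depends on what the sponsor decides.

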2.1 OBJECTIVES AND SCIENTIFIC AIMS

Primary Objectives:

Phase 1:

- To determine the safety, tolerability, maximum tolerated dose (MTD)/recommended phase 2 dose (RP2D) of Debio 1347 Plus Fulvestrant in patients with ER+/HER2-/FGFR amplified metastatic breast cancer

Phase 2:

- To investigate the anti-tumor activity of Debio 1347 in combination with fulvestrant in patients with ER+/HER2-/FGFR-amplified metastatic breast cancer as defined as clinical benefit rate (CBR: Objective Response Rate plus Stable disease \geq 24 weeks)

Secondary objectives:

Phase 1:

- To obtain a preliminary assessment of the anti-tumor activity (CBR and overall response rate (ORR)) of Debio 1347 in combination with fulvestrant in patients with ER+/HER2-/FGFR-amplified metastatic breast cancer

Phase 2:

- To further characterize the safety and tolerability of Debio 1347 in combination with fulvestrant in patients with ER+/HER2-/FGFR- amplified metastatic breast cancer
- To determine the overall response rate (ORR), time to progression (TTP), progression-free survival (PFS) and overall survival (OS) for the combination of Debio 1347 with fulvestrant in patients with ER+/HER2-/FGFR- amplified metastatic breast cancer

Exploratory Objectives:

Phase 1 and Phase 2:

- To measure the pharmacokinetic (PK) parameters of Debio 1347 in combination with fulvestrant
- To measure pharmacodynamic biomarkers of FGFR inhibition
- To make an assessment of biomarkers of response and/or resistance from archival tissue and fresh tumor biopsies (using next generation sequencing, FISH, protein and mRNA expression) and plasma (cell-free DNA) and correlate with clinical benefit

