10.1 EVALUATION DURING TREATMENT/INTERVENTION

	Screening	Treatment							EOT	F/U ^a
Cycle		1				2		3+		Every 12 weeks
Day	-28 to -1	1	4	8	15	28	1	15	1	
		±2	±1	±2	±2	-4	±3	±3	±3	±7
										±14
Written Informed Consent	X									
Review of Eligibility Criteria	X									
Demographic Information	X									
Vital Signs, ECOG PS ^b	X	X			X		X	X	X	X
Height	X									
Physical Exam and Weight	X	X			X		X	X	X	X
12-lead ECG ^c	X	X				X			X	X
ECHO ^c	X								X	X
Haematology and Chemistry blood work ^d	X	X		X	X		X	X	X	X
Tumor markers (CEA and CA15-3)	X	X					X		X	X
Other Bloodwork (CRP LDH, uric acid and γGTP)	X	X		X	X		X	X	X	X
Phosphate (P)			X							
Blood coagulation (PT (INR), APTT)	X	X					X		X	X
Urinalysis ^e	X	X		X	X		X	X	X	X
Calcium regulating hormones bloodwork ^f	X	X					X		X	X
Serum pregnancy test	X									X
Ophthalmological testing ^g	X									X
Adverse events		X		X	X	X	X	X	X	

Fulvestrant		X			X	X			X		
Tumour assessment^h	X								X	X	
Plasma sample for CfDNAⁱ		X			X				X	X	
Pharmacokinetics^j		X			X		X		X		
Tumor Biopsy^k	X										
HepBsAg, HepBcAb, HIV and hepatitis C antibody^l	X										

Abbreviations: DEXA, dual-energy X-ray absorptiometry; ECHO, echocardiogram; ECOG, Eastern Cooperative Oncology Group; EOS, end-of-study; EOT, end-of-treatment (any study treatment); IV, intravenous; PS, performance status.

- a) Survival and disease status will be assessed every 12 weeks (+/- 14 days) until death, withdrawal of consent, or end of the study, whichever is first. Assessments can be collected through phone call or review of patient records.
- b) Blood pressure and heart rate to be collected. BP and pulse rate to be taken after at least 5 minutes of supine rest.
- c) ECG recorded every 3RD cycle *after* Cycle 3. If an ECG shows QTc prolongation (> 470 msec.), the ECG must be repeated twice additionally to obtain values in triplicate. ECHO will be done at baseline, every 3 cycles and at EOT during the phase 1 portion of the study.
- d) Haematology: red blood cells, haemoglobin, hematocrit, platelet count, white blood cells, neutrophils, lymphocytes, monocytes, eosinophils, basophils.
- Blood chemistry(Fasting): total protein, albumin, total bilirubin, AST, ALT, LDH, ALP, γ GTP, CK, total cholesterol, sodium (Na), potassium (K), calcium (Ca), chloride (Cl), phosphate (P), magnesium (Mg), creatinine, BUN, CRP, uric acid, glucose.
- e) Urinalysis: protein, blood, glucose, urobilinogen, pH, sediment, creatinine, calcium (Ca), phosphate (P).

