Simon's two-stage optimal design will be used to study the treatment efficacy since it permits early termination of the study. We will allow early termination only if the data at the first stage indicate that the treatment is highly inactive. 18 patients will initially enter the study. If there are 2 or fewer patients with clinical benefit (CR, PR or SD \geq 24) observed, the study will be terminated early and declared to have a negative result. If 3 or more patients have clinical benefit, enrollment will be extended to 43 patients. Note, we will halt the trial after the first stage while awaiting results from the first 18 patients.

If 8 or more patients with clinical benefit are observed among the 43 patients, the study will be considered to have a positive result and this regimen would be considered worthy of further testing in this disease. The probability of early termination is 0.73 if the true clinical benefit probability is \leq 10%. This design would effectively discriminate between true clinical benefit rates of \leq 10% and \geq 25%. This design has 80% power and a type I error of 5%.

Upon completion of the study, the true clinical benefit rate will be estimated via the observed rate and an exact confidence interval will be constructed.

The maximum of 43 patients requires about 2 years of patient accrual with an anticipated enrollment of 1-2 patients per month.

In secondary analyses for the Phase Ib portion of the trial, the ORR will be summarized as a proportion with a 95% exact confidence interval. TTP, PFS and OS will be evaluated using Kaplan-Meier methods. All toxicities as measured by the NCI CTCAE Version 4.0, will be described by frequency and grade, by cycle and over all cycles, with the maximum grade over all cycles used as the summary measure per patient. All patients will be included in the safety analyses regardless of whether a patient is not evaluable for the efficacy endpoint.

All exploratory analyses will be conducted for each phase of the trial separately. PK/PD measures such as AUC, Cmax, and Cmin will be calculated and summarized. Exploratory endpoints that aim to investigate biomarkers of clinical benefit and/or resistance will be evaluated descriptively and graphically. If there are a sufficient number of clinical benefit events, nonparametric tests (Fisher's exact or Wilcoxon rank sum) will be used to test the exploratory hypotheses depending on the distribution of the biomarker.

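### Section 13.1 puts a 2-year limit on survival follow-up that Section 10.1.2 and the schedule do not have; if followed, it thins late OS data and may bias OS beyond 24 months

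*Combined protocol and SAP*

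**What the plan says.** Section 2.1 lists among the phase 2 secondary objectives "time to progression (TTP), progression-free survival (PFS) and overall survival (OS) for the combination of Debio 1347 with fulvestrant". Three places govern how survival is collected.

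- **Section 13.1.** Entry: "After documented disease progression, each subject will be followed by telephone for overall survival". End: the same sentence has patients "followed by telephone for overall survival until death, withdrawal of consent, the end of the study, or 2 years, whichever occurs first".
- **Section 10.1.2.** Entry: "Once a subject experiences confirmed disease progression or starts a new anti-cancer therapy, the subject moves into the survival follow-up phase". End: contact is "every 12 weeks to assess for survival status until death, withdrawal of consent, or the end of the study, whichever occurs first".
- **Schedule in Section 10.1, footnote a.** "Survival and disease status will be assessed every 12 weeks (+/- 14 days) until death, withdrawal of consent, or end of the study". It gives no 2-year limit and no progression trigger.

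On analysis, Section 14.0 says "TTP, PFS and OS will be evaluated using Kaplan-Meier methods". The lead-in to that passage names the phase Ib portion, but no other OS method is given. Section 14.0 contains no censoring rule for OS, and the supplied text does not define the end of the study.

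**The concern.** A coordinator with a patient alive 25 months after progression must keep calling under 10.1.2 and footnote a, and may stop under 13.1. The rules cannot both be followed.

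The 13.1 version also has a statistical consequence. If the 2 years run from progression, the censoring time is progression time plus 24 months. A patient who progresses at month 2 is censored at month 26, and one who progresses at month 12 at month 36. Kaplan-Meier assumes that patients censored at a given time have the same outlook as those still followed. Here the censored are the earliest progressors, so that assumption is in doubt. The affected region starts close to where OS might be read: Section 3.1.1 cites a median of 26.4 months for fulvestrant 500 mg.

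The entry triggers differ as well. Read alone, 13.1 ends disease follow-up when a non-study cancer treatment begins and opens survival follow-up only at documented progression. A patient who changes therapy before progressing therefore has no OS follow-up under that section.

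**Working it through.** The documents state no OS figure to reproduce. The only computed design figures are those of the Simon design in Section 14.0. They check (early termination 0.734, power 0.800, exact type I error 0.048) and are not inputs here.

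**Inputs.**
- From the documents: 43 patients and about 24 months' accrual (Section 14.0); median PFS 6.5 months and median OS 26.4 and 22.3 months (Section 3.1.1); median PFS 3.8 and 9.2 months (Section 3.1.2).
- Assumed: the shape of post-progression survival, its mean or median, its dependence on progression time, and the data cut.

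**1. Number at risk.** Let progression time T be exponential with median 6.5 months, so a = ln 2/6.5 = 0.1066. Let post-progression survival R be exponential with an assumed mean of 26 months, so b = 1/26 = 0.0385, independent of T. Ignore death before progression. This gives a median OS of about 28 months.

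Without the limit, S(t) = e^(−at) + [a/(a−b)]·[e^(−bt) − e^(−at)].
- S(36) = 0.0215 + 1.564 × (0.2504 − 0.0215) = 0.380, and 43 × 0.380 = 16.3 patients.

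With the limit, a patient still observed at t must also have T ≥ t − 24. This gives C(t) = e^(−at) + [a/(a−b)]·e^(−bt)·[e^(−(a−b)(t−24)) − e^(−(a−b)t)].
- C(36) = 0.0215 + 1.564 × 0.2504 × (0.4412 − 0.0859) = 0.161, and 43 × 0.161 = 6.9 patients.

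At 24 months the two agree (0.578, or 24.8 patients), because nobody can be censored by the limit earlier. With a cut 60 months after first entry every patient has at least 36 months of potential follow-up, so 16.3 against 6.9 is the effect of the limit alone. Simulated trials gave 16.3 and 6.9. At 48 months they gave 5.2 and 0.9.

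**2. Share censored by the limit.** This is P(R > 24) = e^(−24/26) = 0.397, times the probability that T + 24 falls before the data cut.

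| Cut after first entry | Share in this model | Patients of 43 | Range over other inputs |
|---|---|---|---|
| 36 months | 0.397 × 0.218 = 8.7% | 3.7 | 5–13% |
| 48 months | 0.397 × 0.639 = 25% | 10.9 | 20–34% |
| 60 months | 0.397 × 0.900 = 36% | 15.4 | 36–45% |

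The range uses PFS medians 3.8–9.2 months, post-progression medians 20–24 months, and correlation 0 or 0.5.

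**3. Bias.** Entries are Kaplan-Meier OS with the limit minus OS without it, in percentage points, from 400,000 simulated patients.

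| Assumption after progression | 36 months | 48 months |
|---|---|---|
| Constant hazard, unrelated to T (PFS 3.8–9.2, OS 22.3–35; 35 is assumed) | +0.1 to +1.2 | +0.3 to +2.7 |
| Shared gamma frailty, variance 0.25–1.0 | +1.8 to +2.3 | +4.5 to +5.5 |
| Correlation 0.5 between T and R | +3 to +5 | +8 to +11 |
| Rising hazard (Weibull shape 1.3–1.6) | +2.1 to +3.4 | +4.3 to +6.1 |
| Death hazard unrelated to progression | 0 | 0 |
| Falling hazard (Weibull shape 0.6), unrelated to T | −0.9 | −2.6 |
| Frailty in R only, variance 1.0 | −1.1 | −3.3 |

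The constant-hazard case is slightly positive because those still followed late include patients not yet progressed, who in this model carry no death hazard.

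**4. Median.** In the frailty and Weibull scenarios, calibrated to a 26.4-month median, it moves by at most 0.2 months. In the correlated scenarios nearest that value it goes from 25.1 to 25.1 and from 28.6 to 29.1. Larger shifts (32.6 to 35.3, 36.0 to 40.0) need a true median 6 to 10 months above the benchmark.

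**The case against.** Several points on the other side are sound.

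- **Clock origin.** Section 13.1 does not say what the 2 years run from. Progression is the natural reading of the sentence, not a stated rule, and the censoring arithmetic depends on it. The ambiguity is itself a reason to clarify.
- **Direction.** A reader might infer that the limit necessarily inflates late OS. The documents do not support that. They give no information on post-progression survival or its dependence on progression time, and the table above contains zero and negative cases.
- **Share affected.** A reader might take it that nearly half of patients would be censored by the limit. Figures of 44–50% arise only in a study with no end. All three rules also stop at the end of the study, which is undefined, so the share is a range.
- **Precision.** With 43 patients and OS near 0.4 at 36 months, the standard error under complete follow-up is √(0.4 × 0.6/43) = 0.075. A bias of 1 to 5 points lies within that. OS has no hypothesis or decision rule, and if the trial stops at stage 1 only 18 phase 2 patients contribute.
- **New-therapy gap.** Section 10.1.2 explicitly follows patients who start a new therapy, and footnote a has no progression trigger. Section 13.1 omits these patients but does not forbid following them, so the documents do not show that they would be lost. The gap arises only if 13.1 is applied alone.

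These points limit the size of the problem. They do not remove the conflict between the sections or the loss of late follow-up if 13.1 governs.

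**Conclusion.** The inconsistency is plain on the text: 13.1 limits survival follow-up to 2 years and starts it at progression, while 10.1.2 and footnote a set no such limit and 10.1.2 has a wider entry trigger.

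If 13.1 is followed and its clock starts at progression, censoring depends on a prognostic event, and OS beyond 24 months may be biased, most likely upward. The better-supported cost is information: the number at risk at 36 months falls by more than half under the assumed exponential model with a 60-month cut. An earlier cut makes the effect smaller.

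It would be too strong to say that the median is materially overstated, since it hardly moves near the cited 26.4 months. OS up to 24 months and the primary clinical benefit analysis are unaffected. This is an inexpensive correction to a secondary endpoint, and no threat to the trial's main conclusion.

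**What to change.** Use one survival follow-up rule in Section 13.1, Section 10.1.2 and schedule footnote a:

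1. Remove the 2-year limit from the OS sentence in 13.1, so that follow-up ends at death, withdrawal of consent or end of study as in the other two places.
2. In 13.1, start OS follow-up at progression or new anti-cancer therapy, whichever comes first, to match 10.1.2.
3. Define the end of the study, and state the OS censoring rule in Section 14.0.
4. If a limit must stay, count it from Cycle 1 Day 1 for every patient, so that censoring is administrative, and report OS only up to that limit.

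The cost is a short amendment plus some further 12-weekly calls or chart reviews for long survivors, which 10.1.2 already requires.
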